8.2.5.4 Summaries of Baseline Characteristics and Demographics

The comparability of the treatment groups for each relevant characteristic will be assessed by the use of tables and/or graphs in all subjects as well as in subjects with PD-L1 positive expression. No statistical hypothesis tests will be performed on these characteristics. The number and percentage of subjects randomized, and the primary reason for discontinuation

will be displayed. Demographic variables (such as age) and baseline characteristics will be summarized by treatment either by descriptive statistics or categorical tables. The reasons for exclusion from the ITT population (if any) will be summarized.

8.2.6 Multiplicity

The overall type I error rate is strongly controlled at 2.5% (one-sided) with:

- 0.19% allocated to each PFS hypothesis of pembrolizumab monotherapy vs. standard treatment (H1) and pembrolizumab in combination with chemotherapy vs. standard treatment (H4) in subjects with PD-L1 CPS 20;
- 0.02% allocated to PFS hypothesis of pembrolizumab in combination with chemotherapy vs. standard treatment in all subjects (H6);
- 0.7% allocated to each OS hypothesis of pembrolizumab monotherapy vs. standard treatment (H7) and pembrolizumab in combination with chemotherapy vs. standard treatment (H11) in subjects with PD-L1 CPS 20;
- 0.7% allocated to OS noninferiority hypothesis of pembrolizumab in combination with chemotherapy vs. standard treatment in all subjects (H13).

For the PFS hypotheses of pembrolizumab monotherapy vs. standard treatment, a fixed sequential testing will be applied in the order of PFS superiority in subjects with PD-L1 CPS 20 (H1), in subjects with PD-L1 CPS 1 (H2), and in all subjects (H3).

For the PFS hypotheses of pembrolizumab in combination with chemotherapy vs. standard treatment, a fixed sequential testing will be applied in the order of PFS superiority in subjects with PD-L1 CPS 20 (H4) and in subjects with PD-L1 CPS 1 (H5). If H5 is rejected, then the corresponding alpha will be fully shifted to PFS superiority hypothesis for all subjects (H6).

If any of the PFS null hypotheses in all subjects (H3 and H6) is rejected, the corresponding alpha level will be shifted and distributed to the OS hypotheses for the corresponding experimental treatment using the graphical approach of Maurer and Bretz (2013) [57].

For the OS hypotheses of pembrolizumab monotherapy vs. standard treatment, a fixed sequential testing will be applied in the order of OS superiority in subjects with PD-L1 CPS 20 (H7), OS superiority in subjects with PD-L1 CPS 1 (H8), OS noninferiority in all subjects (H9) and OS superiority in all subjects (H10). If H10 is rejected, then the corresponding alpha will be essentially fully reallocated and distributed equally to H11 and H13 if not already significant, with a very small fraction (0.002) reallocated to H1.

[figure not shown]
For the OS hypotheses of pembrolizumab in combination with chemotherapy vs. standard treatment, a fixed sequential testing will be applied in the order of OS superiority in subjects with PD-L1 CPS 20 (H11) and OS superiority in subjects with PD-L1 CPS 1 (H12). If H12 is significant, the corresponding alpha will be shifted fully to OS noninferiority in all subjects (H13). If H14 is rejected, then the corresponding alpha will be essentially fully reallocated to H7 if not already significant, with a very small fraction (0.001) reallocated to H4.

The alpha reallocation strategy will follow the graphical approach of Maurer and Bretz (2013) [57]. Note that if the α -reallocation from OS hypothesis testing occurs at the final analysis after hypothesis testing for PFS has been completed, the previously computed p-values for the

PFS analyses can be compared to the updated bounds if the PFS hypotheses are not already significant.

Figure 3 displays the multiplicity strategy diagram for the study.

Figure 3 Multiplicity Strategy

8.2.7 Sample Size and Power Calculation

The study plans to randomize approximately 825 subjects with 1:1:1 ratio into the treatment groups of pembrolizumab monotherapy, a combination of pembrolizumab with chemotherapy and standard treatment, stratified by PD-L1 expression (strongly positive vs. not strongly positive), HPV status (HPV+ vs. HPV-), and ECOG performance status (0 vs. 1). The prevalence of PD-L1 positive subpopulation is projected to be 50% for PD-L1 CPS 20 and 80% for the PD-L1 CPS 1 subpopulation.

Two interim efficacy analyses are planned in this study. A Hwang-Shih-DeCani alpha-spending function with gamma parameter (-4) is constructed to implement group-sequential efficacy boundaries for each PFS and each OS hypothesis.

PFS:

Two PFS analyses are planned at interim analyses 1 and 2. The PFS hypotheses will be tested at interim analysis 1, and a second test of PFS, which will be the final PFS analyses, may occur at interim analysis 2 only if superior PFS is not declared at interim analysis 1. At the time of the final PFS analysis:

H1, H4: for subjects with PD-L1 CPS 20, it is expected that approximately 237 PFS events will have been observed between one experimental treatment and standard treatment.

The study has 90% power with each experimental treatment (pembrolizumab monotherapy [H1] or pembrolizumab in combination with chemotherapy [H4]) to detect a hazard ratio of 0.58 vs. standard treatment at alpha = 0.19% (one-sided).

H2, H5: for subjects with PD-L1 CPS 1, it is expected that approximately 378 PFS events will have been observed between one experimental treatment and standard treatment.

The study has 98.6% power with each experimental treatment (pembrolizumab monotherapy [H2] or pembrolizumab in combination with chemotherapy [H5]) to detect a hazard ratio of 0.59 vs. standard treatment at alpha = 0.19% (one-sided). (Note that H2 will be tested only if H1 is rejected and H5 will be tested only if H4 is rejected.)

H3: for all subjects: it is expected that approximately 474 PFS events will have been observed between pembrolizumab monotherapy and standard treatment. The study has 99.6% power with pembrolizumab monotherapy to detect a hazard ratio of 0.6 vs. standard treatment at alpha = 0.19% (one-sided). (Note that H3 will be tested only if H1 and H2 are rejected under the multiplicity strategy.)

H6: for all subjects, it is expected that approximately 474 PFS events will have been observed between pembrolizumab in combination with chemotherapy and standard treatment. The study has 97.7% power with pembrolizumab in combination with chemotherapy to detect a hazard ratio of 0.6 vs. standard treatment at alpha = 0.02% (one-sided).

The PFS sample size calculation is based on the following assumptions: 1) progression-free survival follows an exponential distribution with a median of 6 months in the standard treatment arm; 2) hazard ratios are 0.58 for subjects with PD-L1 CPS 20, 0.59 for subjects with PD-L1 CPS 1 and 0.6 for all subjects; 3) an enrollment period of 21 months; 4) at least 9 months follow-up at interim analysis 1, and 17 months follow-up at interim analysis 2; and 5) a yearly dropout rate of 5%.

OS

Three OS analyses are planned at interim analyses 1, 2 and the final analysis. At the time of the final analysis:

H7, H11: for subjects with PD-L1 CPS 20, it is expected that approximately 222 deaths will have been observed between one experimental treatment and standard treatment.

The study has 90.5% power with each experimental treatment (pembrolizumab monotherapy [H7] or pembrolizumab in combination with chemotherapy [H11]) to detect a hazard ratio of 0.6 vs. standard treatment at alpha = 0.7% (one-sided).

H8, H12: for subjects with PD-L1 CPS 1, it is expected that approximately 359 deaths will have been observed between one experimental treatment and standard treatment. The

study has 94.3% power with each experimental treatment (pembrolizumab monotherapy [H8] or pembrolizumab in combination with chemotherapy [H12]) to detect a hazard ratio of 0.65 vs. standard treatment at alpha = 0.7% (one-sided). (Note that H8 will be tested only if H7 is rejected and H12 will be tested only if H11 is rejected.)

H9, H13: for all subjects, it is expected that approximately 455 deaths will have been observed between one experimental treatment and standard treatment. The study has 87.85% power with a hazard ratio of 0.85 to establish noninferiority (NI margin = 1.2) for each experimental treatment (pembrolizumab monotherapy [H9] or pembrolizumab in combination with chemotherapy [H13]) vs. standard treatment at alpha = 0.7% (one-sided). (Note that H9 will be tested only if H7 and H8 are rejected under the multiplicity strategy.)

H10, H14: for all subjects, it is expected that approximately 455 deaths will have been observed between one experimental treatment and standard treatment. The study has 90.4% power with each experimental treatment (pembrolizumab monotherapy [H10] or pembrolizumab in combination with chemotherapy [H14]) to detect a hazard ratio of 0.7 vs. standard treatment at alpha = 0.7% (one-sided). (Note that H10 will be tested only if H7 through H9 are rejected under the multiplicity strategy and H14 will be tested only if noninferiority is established for H13.)

The OS sample size calculation is based on the following assumptions: 1) overall survival follows an exponential distribution with a median of 10 months in the standard treatment arm; 2) the hazard ratios are 0.6 for subjects with PD-L1 CPS 20, 0.65 for subjects with PD-L1 CPS 1, 0.7 for all subjects for the superiority hypotheses, and 0.85 for all subjects for the noninferiority hypotheses; 3) an enrollment period of 21 months; 4) at least 23 months follow-up; and 5) a yearly dropout rate of 2%.

The assumptions for median PFS of 6 months and median OS of 10 months in the standard treatment arm are based on median PFS and median OS estimates from the EXTREME trial [40; 54]. The assumptions do not take into account potential prognostic implications in a biomarker selected population. As such, the median of the standard treatment for the PD-L1 positive subgroup may be more or less than 6 months for PFS, and more or less than 10 months for OS.

The sample size and power calculations were performed in the software EAST 6 and R (package “gsDesign”).

8.2.8 Subgroup Analyses and Effect of Baseline Factors

To determine whether the treatment effect is consistent across various subgroups, the estimate of the between-group treatment effect (with a nominal 95% CI) for the primary endpoint will be estimated and plotted by treatment group within each category of the following classification variables:

- Stratification factors
 - PD-L1 subgroup (strongly positive vs. not strongly positive, defined by TPS 50%)

- HPV status (HPV-positive vs. HPV-negative)
- ECOG status (0 vs. 1)
- PD-L1 expression level defined by CPS (≥ 20 vs. not ≥ 20 ; and ≥ 1 vs. not ≥ 1)
- Age category (<65 vs. ≥ 65 years)
- Sex (female vs. male)
- Race (white vs. non-white)
- Region (NA vs EU vs ROW)
- Smoking status (never vs. former vs. current)
- Disease status (recurrent vs. metastatic)

In addition, a Forest plot will be produced, which provides the estimated point estimates and confidence intervals for the treatment effect across the categories of subgroups listed above.

The consistency of the treatment effect will be assessed descriptively via summary statistics by category for the classification variables listed above.

8.2.9 Interim Analyses

8.2.9.1 Safety Interim Analyses

A formal interim safety analysis will take place after 10 subjects in pembrolizumab in combination with chemotherapy arm have completed 2 cycles of therapy. If the majority of the enrolled subjects (more than 80%) require a dose modification of platinum and/or 5-FU by the end of the 2nd cycle, the dose of the chemotherapies may be reduced for the remainder of the study. If the majority of the participants (more than 80%) require 2 dose modifications of platinum and/or 5-FU by the end of the 2nd cycle, the Sponsor may consider discontinuing the combination arm.

[Table 22](#) below summarizes the probabilities of observing the numbers and percentages of subjects who require 1 dose modification under different assumptions of true dose modification rate θ_0 , which can be interpreted as the p-values for testing the null hypothesis that the true dose modification rate is less than θ_0 . These criteria are considered non-binding guidelines, i.e., a recommendation would not be based solely on statistical grounds, as many other factors (i.e., all aspects of the data from the trial) may be part of the decision process.

Additionally, safety monitoring interim analyses are planned to be conducted approximately every quarter and will commence following the completion of the formal planned safety interim analysis. The number of percentage of subjects with a dose modification, together with AE data, will be summarized. Additional details of the monitoring timing and guidelines will be provided in the DMC charter.

Table 22 Probability of Observing the Number (%) of Subjects who Require a Dose Modification

Observed number (%) of subjects	Probabilities (p-values) under different assumptions				
	$\theta_0 = 0.5$	$\theta_0 = 0.6$	$\theta_0 = 0.7$	$\theta_0 = 0.8$	$\theta_0 = 0.9$
5 (50.0%)	0.377	0.633	0.850	0.967	0.998
6 (60.0%)	0.172	0.382	0.650	0.879	0.987
7 (70.0%)	0.055	0.167	0.383	0.678	0.930
8 (80.0%)	0.011	0.046	0.149	0.376	0.736
9 (90.0%)	0.001	0.006	0.028	0.107	0.349

The probabilities (p-values) for the monitoring of the first 10 subjects who have completed 2 cycles of therapy were calculated from Binomial distribution; and for the quarterly safety monitoring, the probabilities (p-values) can be calculated from asymptotical Normal distribution based on the observed proportion of subjects with a dose modification and the number of subjects at the time of analysis.

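### Table 22 prints the probability of more than k modified subjects as the p-value for observing k, so every row is one count off

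*Combined protocol and SAP*

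**What the plan says.** Section 8.2.9.1 plans a formal safety analysis once 10 combination-arm subjects have completed two cycles. The first criterion begins "If the majority of the enrolled subjects (more than 80%) require a dose modification of platinum and/or 5-FU", by the end of cycle 2, in which case the chemotherapy doses may be lowered from then on. A second criterion uses the same 80% figure for two modifications and may lead the sponsor to consider dropping the arm.

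Table 22 accompanies the one-modification criterion. The text presents its entries as probabilities of observing given numbers of modified subjects, "which can be interpreted as the p-values for testing the null hypothesis that the true dose modification rate is less than" θ0. The rows are headed "Observed number (%) of subjects" and run from 5 (50%) to 9 (90%). The columns are headed "Probabilities (p-values) under different assumptions", with θ0 from 0.5 to 0.9. The footnote says that the values "for the monitoring of the first 10 subjects who have completed 2 cycles of therapy were calculated from Binomial distribution". The section adds: "These criteria are considered non-binding guidelines".

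**The concern.** A p-value for an observed count has to include that count in the tail. The printed figures look too small for their labels. The entry for 9 of 10 at θ0 = 0.9 is 0.349, yet if the true rate is 90%, seeing 9 or 10 of 10 is the expected result and should have a probability well above one half.

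The error has one direction. If the observed count is left out of the tail, every p-value is too small, and a monitoring committee reading the table sees more evidence of a high modification rate than the data carry. The action linked to that evidence is a lower chemotherapy dose in one arm of a Phase III trial.

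**Working it through.** **Inputs, all from Section 8.2.9.1.** n = 10; θ0 = 0.5, 0.6, 0.7, 0.8, 0.9; observed counts k = 5 to 9; binomial distribution; null hypothesis that the rate is below θ0.

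**Formulas.** Let X ~ Bin(10, θ0). Large counts speak against the null, and its boundary value θ0 gives the largest tail probability. The p-value at k is therefore P(X ≥ k) = Σ_{j=k}^{10} C(10, j) θ0^j (1 − θ0)^(10−j). The exceedance probability is P(X > k) = P(X ≥ k) − P(X = k).

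**Step 1: reproduce the printed table.** P(X > k), to four decimals:

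| k | θ0 = 0.5 | 0.6 | 0.7 | 0.8 | 0.9 |
|---|---|---|---|---|---|
| 5 | 0.3770 | 0.6331 | 0.8497 | 0.9672 | 0.9984 |
| 6 | 0.1719 | 0.3823 | 0.6496 | 0.8791 | 0.9872 |
| 7 | 0.0547 | 0.1673 | 0.3828 | 0.6778 | 0.9298 |
| 8 | 0.0107 | 0.0464 | 0.1493 | 0.3758 | 0.7361 |
| 9 | 0.0010 | 0.0060 | 0.0282 | 0.1074 | 0.3487 |

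Rounded to three decimals, these match all 25 printed cells. P(X ≥ k), P(X = k) and the mid-p value each match none.

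**Step 2: the p-values for the labelled counts.** P(X ≥ k):

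| k | θ0 = 0.5 | 0.6 | 0.7 | 0.8 | 0.9 |
|---|---|---|---|---|---|
| 5 | 0.623 | 0.834 | 0.953 | 0.994 | 1.000 |
| 6 | 0.377 | 0.633 | 0.850 | 0.967 | 0.998 |
| 7 | 0.172 | 0.382 | 0.650 | 0.879 | 0.987 |
| 8 | 0.055 | 0.167 | 0.383 | 0.678 | 0.930 |
| 9 | 0.011 | 0.046 | 0.149 | 0.376 | 0.736 |
| 10 | 0.001 | 0.006 | 0.028 | 0.107 | 0.349 |

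Rows 6 to 10 here are the printed rows 5 to 9.

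**Step 3: hand check of three cells.**
- k = 9, θ0 = 0.9: the printed 0.349 is 0.9^10 = 0.3487, the chance of 10 of 10. Adding P(X = 9) = 10 × 0.9^9 × 0.1 = 0.3874 gives 0.7361.
- k = 9, θ0 = 0.7: 0.7^10 = 0.0282, as printed. Adding 10 × 0.7^9 × 0.3 = 0.1211 gives 0.149.
- k = 9, θ0 = 0.8: 0.8^10 = 0.1074, as printed. Adding 10 × 0.8^9 × 0.2 = 0.2684 gives 0.376.

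**Step 4: size of the error.** Each cell is too small by P(X = k). Across the table this runs from 0.0015 (k = 5, θ0 = 0.9) to 0.3874 (k = 9, θ0 = 0.9).

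**The case against.** The best defence is that the binomial arithmetic is sound and that exceedance may have been intended. Nine of 10 is the smallest count above 80%, so row 8, P(X > 8), is exactly the chance that the first criterion is met at each true rate. That stands: as trigger probabilities the row 8 figures are valid. It does not rescue the table, because the row heading, the column heading, the text and the footnote speak of observed counts or p-values, and none of them says that the labelled count is excluded. On this reading the labels are wrong instead of the numbers.

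The second defence is that little depends on the table. This stands too, and it sets the severity. The criterion is a count with no p-value threshold, so 9 of 10 meets it under either labelling. The criteria do not bind. Section 4.3 reports that the early safety look has taken place and that the monitoring committee, most recently in February 2017, recommended no changes.

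A reader might infer three stronger points, which the documents do not support:

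- *The error moves results across a significance line.* Some cells would cross 0.05, but the plan sets no level for this table.
- *The quarterly Normal p-values use a different tail from the formal look.* The footnote says only that they are "based on the observed proportion of subjects with a dose modification and the number of subjects at the time of analysis". With the variance under θ0, the Normal value lies between the two binomial probabilities in the cases checked, and neither is always nearer. For 42 of 50 against 80%, z = (0.84 − 0.80)/√(0.16/50) = 0.707 and p = 0.240, against P(X ≥ 42) = 0.307 and P(X > 42) = 0.190. For 45 of 50 it is 0.039, against 0.048 and 0.018. With the variance at the observed proportion, 45 of 50 gives z = 0.10/√(0.09/50) = 2.357 and p = 0.009, below both. No systematic mismatch follows.
- *The criteria and the table use different denominators.* The criteria speak of enrolled subjects and participants, the footnote of two-cycle completers. The sentence that opens the section sets the look at 10 completers, and the natural reading is that the same 10 are meant throughout. Nothing in the documents shows a bias or its direction.

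**Conclusion.** Table 22 is wrong as written. Read as the plan says to read it, each row understates the p-value by the probability of the observed count itself. At 9 of 10, where the criterion is first met, the printed 0.028 against 70% should be 0.149 (0.149/0.028, about 5 times larger) and the printed 0.107 against 80% should be 0.376 (about 3.5 times). At 8 of 10 against 60%, 0.046 should be 0.167 (about 3.6 times). A reader would take 9 of 10 as fairly strong evidence that the true rate exceeds 70%, and it is not.

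The conclusion rests only on the binomial model, the sample of 10 and the null hypothesis stated in the section; no outside figure is assumed. Severity is minor, for the reasons conceded above. Table 22 also covers only the one-modification criterion, and no efficacy alpha or power is affected.

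**What to change.** Change the row labels of Table 22 from 5–9 (50%–90%) to 6–10 (60%–100%). Every printed value is then the correct p-value, and nothing needs recalculating. The row for 5 of 10 drops out, which does not matter for a criterion above 80%.

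If exceedance probabilities are what the sponsor wants, keep the numbers, label the rows as *more than k*, and delete both the p-value wording in the column heading and footnote and the null-hypothesis interpretation in the text.

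The cost is one relabelled column or a few deleted words, with no data work. Under the first option 9 of 10 carries weaker formal evidence than printed, so a decision at that count would lean more on the adverse event data, which the section already asks to be considered.

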8.2.9.2 Efficacy Interim Analyses

Two interim analyses are currently planned. Results will be reviewed by an external DMC. Further details of interim analyses are provided below and will be incorporated into the DMC charter.

For each PFS and each OS hypothesis, a Hwang-Shih-DeCani alpha-spending function with gamma parameter (-4) is constructed to implement group-sequential efficacy boundaries to control the type I error. The same spending function used for OS superiority hypotheses is also implemented to calculate boundaries for the noninferiority hypotheses. [Table 23](#) provides more details on the timing, number of events and decision guidance for each analysis. The actual boundaries and the alpha level will be determined from the overall alpha level after alpha shifting as a result of a successful analysis and the actual number of events observed at the time of the interim analysis using the corresponding alpha-spending function.

In the event that superiority is declared for one or more PFS hypotheses at interim analysis 1, the study will continue to follow subjects for OS unless substantial treatment effect is demonstrated for all OS hypotheses at the significance level determined from the alpha-spending function as specified above.

Interim Analysis 1: interim PFS/OS analyses

The interim analysis will take place when all subjects have been followed up for at least 9 months.

Assuming 21 months enrollment period for 825 all subjects, interim analysis 1 is projected to occur 30 months after study start. The primary objective of the analyses is to demonstrate PFS superiority of pembrolizumab (monotherapy or in combination with chemotherapy).

At the time of interim analysis 1, the expected numbers of PFS events observed for the PFS hypotheses are specified below. If the actual number of events for a PFS hypothesis is different, the spending function boundaries will be adjusted accordingly for the actual number of events for that PFS hypothesis.

- ~211 PFS events between one experimental treatment and standard treatment in subjects with PD-L1 CPS 20 (H1 and H4)
- ~337 PFS events between one experimental treatment and standard treatment in subjects with PD-L1 CPS 1 (H2 and H5)
- ~423 PFS events between one experimental arm and standard treatment in all subjects (H3 and H6)

For the hypotheses of PFS superiority of one experimental treatment in subjects with PD-L1 CPS 20 (H1 and H4), alpha level of 0.19% is allocated to the test. The boundary to demonstrate PFS superiority of one experimental treatment over standard treatment corresponds to a one-sided p-value of 0.0012, which corresponds to an approximate observed hazard ratio of ~0.6585 or less (approximately a 3.11-month or greater improvement over the median PFS from 6 months in the standard treatment arm).

If H1 is rejected, for the hypothesis of PFS superiority of pembrolizumab monotherapy in subjects with PD-L1 CPS 1 (H2), alpha level of 0.19% is shifted from H1. Similarly, if H4 is rejected, for the hypothesis of PFS superiority of pembrolizumab combination therapy in subjects with PD-L1 CPS 1 (H5), alpha level of 0.19% is shifted from H4. The boundary to demonstrate PFS superiority of one experimental treatment over standard treatment in subjects with PD-L1 CPS 1 corresponds to a one-sided p-value of 0.0012, which corresponds to an approximate observed hazard ratio of ~0.7186 or less (approximately a 2.35-month or greater improvement over the median PFS from 6 months in the standard treatment arm).

If H1 and H2 are rejected, for the hypothesis of PFS superiority of pembrolizumab monotherapy in all subjects (H3), alpha level of 0.19% is shifted from H2. The boundary to demonstrate PFS superiority of pembrolizumab monotherapy over standard treatment in all subjects corresponds to a one-sided p-value of 0.0012, which corresponds to an approximate observed hazard ratio of ~0.7446 or less (approximately a 2.05-month or greater improvement over the median PFS from 6 months in the standard treatment arm).

For the hypothesis of PFS superiority of pembrolizumab in combination with chemotherapy in all subjects (H6), alpha level of 0.02% is allocated to the test. The boundary to demonstrate PFS superiority of the experimental treatment over standard treatment corresponds to a one-sided p-value of 0.0001, which corresponds to an approximate observed hazard ratio of ~0.7007 or less (approximately a 2.56-month or greater improvement over the median PFS from 6 months in the standard treatment arm).

The trial will also examine OS at interim analysis 1. The expected numbers of events for the OS hypotheses are:

- ~171 deaths between one experimental arm and standard treatment in subjects with PD-L1 CPS 20 (H7 and H11)
- ~278 deaths between one experimental arm and standard treatment in subjects with PD-L1 CPS 1 (H8 and H12)

- ~352 deaths between one experimental arm and standard treatment in all subjects (H9, H10, H13 and H14)

The hazard ratio at bound, significance level and Z statistics of OS hypotheses provided in [Table 23](#) are based on a nominal overall one-sided alpha level of 0.7% each to pembrolizumab monotherapy vs. standard treatment, and pembrolizumab in combination with chemotherapy vs. standard treatment, though the overall alpha levels for the OS hypotheses may be more than 0.7% due to alpha shifting as a result of success in other hypotheses. The actual alpha level for an OS hypothesis will be recalculated if the overall alpha level is not the same as the specified nominal alpha level given the multiplicity strategy or the expected number of deaths is not observed.

Interim Analysis 2: interim OS analyses and final PFS analyses

The interim analysis will take place when all subjects have been followed up for at least 17 months.

Assuming 21 months enrollment period for 825 all subjects, interim analysis 2 is projected to occur 38 months after study start. The primary objective of the analyses is to demonstrate OS superiority of pembrolizumab (monotherapy or in combination with chemotherapy).

The expected numbers of events for the OS hypotheses are:

- ~205 deaths between one experimental arm and standard treatment in subjects with PD-L1 CPS 20 (H7, H11);
- ~332 deaths between one experimental arm and standard treatment in subjects with PD-L1 CPS 1 (H8, H12);
- ~421 deaths between one experimental arm and standard treatment in all subjects (H9, H10, H13 and H14).

However, if the expected number of events for an OS hypothesis is not observed, then the spending function boundaries will be adjusted accordingly for the smaller number of events for that OS hypothesis.

For the hypotheses of OS superiority of one experimental treatment in subjects with PD-L1 CPS 20 (H7 and H11), an alpha level of 0.7% is allocated to each test. The boundary to demonstrate OS superiority of one experimental treatment over standard treatment in PD-L1 CPS 20 corresponds to a one-sided p-value of 0.0041, which corresponds to an approximate observed HR of ~0.6914 or less (approximately a 4.46-month or greater improvement over the median OS from 10 months in the standard treatment arm).

If H7 is rejected, for the hypothesis of OS superiority of pembrolizumab monotherapy in subjects with PD-L1 CPS 1 (H8), an alpha level of 0.7% is shifted from H7. Similarly, if H11 is rejected, for the hypothesis of OS superiority of pembrolizumab combination therapy in subjects with PD-L1 CPS 1 (H12), alpha level of 0.7% is shifted from H11. The boundary to demonstrate OS superiority of one experimental treatment over standard treatment in PD-L1 CPS 1 corresponds to a one-sided p-value of 0.0041, which corresponds to an approximate observed hazard ratio of ~0.7479 or less (approximately a 3.37-month or greater improvement over the median OS from 10 months in the standard treatment arm).

If H7 through H9 are rejected, for the hypothesis of OS superiority of pembrolizumab monotherapy in all subjects (H10), alpha level of 0.7% is shifted from H9. The boundary to demonstrate OS superiority of pembrolizumab monotherapy over standard treatment in all subjects corresponds to a one-sided p-value of 0.0041, which corresponds to an approximate observed hazard ratio of ~0.7727 or less (approximately a 2.94-month or greater improvement over the median OS from 10 months in the standard treatment arm).

For the hypothesis of OS superiority of pembrolizumab in combination with chemotherapy in all subjects (H14), an alpha level of 0.7% is shifted to the test from H13. The boundary to demonstrate OS superiority of pembrolizumab in combination with chemotherapy over standard treatment in all subjects is same as the boundary for testing OS superiority of pembrolizumab monotherapy over standard treatment in all subjects.

A second test of PFS, which is the final PFS analysis, will be conducted at interim analysis 2 only if superior PFS is not declared for that hypothesis at interim analysis 1. The expected numbers of PFS events at interim analysis 2 are:

- ~237 PFS events between one experimental treatment and standard treatment in subjects with PD-L1 CPS 20 (H1 and H4)
- ~378 PFS events between one experimental treatment and standard treatment in subjects with PD-L1 CPS 1 (H2 and H5)
- ~474 PFS events between one experimental treatment and standard treatment in all subjects (H3 and H6)

If the expected number of PFS events is not observed by the time the analysis is conducted, the remaining alpha as defined by the spending function will be accelerated to the analysis at that time, and the success boundary for PFS will be recalculated for the actual number of events observed at that time considering the correlation between the interim and final PFS analyses data. Likewise, if the timing of events occurs faster than anticipated, the test boundary at the final PFS analysis will be adjusted to use the remaining Type I error not spent at earlier analysis.

Final Analysis: final OS analyses

The final analysis will take place when:

- 1) At least 222 deaths are observed between one experimental treatment and standard treatment in subjects with PD-L1 CPS 20 (H7 and H11);
- 2) At least 359 deaths are observed between one experimental treatment and standard treatment in subjects with PD-L1 CPS 1 (H8 and H12);
- 3) At least 455 deaths are observed between one experimental treatment and standard treatment in all subjects (H9, H10, H13 and H14);
- 4) All subjects have been followed up for at least 23 months.

The final analysis is expected to occur ~44 months after study start. For any hypothesis listed above, if superiority has not been declared at IA1 or IA2, the specified number of deaths is to be observed for the final analysis. If the expected number of deaths for a hypothesis is not observed by the time that the trial is open for 44 months, the timing of the final analysis may

be delayed for up to 2 months or when the target death event numbers are observed, whichever occurs first. This calendar trigger will enable a suitable follow-up after IA2 and prevent the trial from continuing to an unreasonable duration. If at the time of the final analysis, the number of deaths for one hypothesis is not the same as specified above, the boundary at the final analysis will be adjusted to use the remaining Type I error not spent at earlier analyses.

Table 23 Decision Guidance at Each Analysis

Timing of Analysis	Testing	Expected number of events	Value at boundary	Efficacy Boundary [†]
IA1 (interim PFS analyses and interim OS analyses)				
30 mos. from study start; all 825 subjects enrolled and followed up for at least 9 months	PFS mono/combo vs. SOC in subjects with PD-L1 CPS 20 (H1/H4)	~211	Z statistic p-value (one-sided) Approx. observed HR	3.0329 0.0012 0.6585
	PFS mono/combo vs. SOC in subjects with PD-L1 CPS 1 (H2/H5)	~337	Z statistic p-value (one-sided) Approx. observed HR	3.0304 0.0012 0.7186
	PFS mono vs. SOC in all subjects (H3)	~423	Z statistic p-value (one-sided) Approx. observed HR	3.0304 0.0012 0.7446
	PFS combo vs. SOC in all subjects (H6)	~423	Z statistic p-value (one-sided) Approx. observed HR	3.6551 0.0001 0.7007
	OS mono/combo vs. SOC in subjects with PD-L1 CPS 20 (H7/H11)	~171	Z statistic p-value (one-sided) Approx. observed HR	2.7808 0.0027 0.6531
	OS mono/combo vs. SOC in subjects with PD-L1 CPS 1 (H8/H12)	~278	Z statistic p-value (one-sided) Approx. observed HR	2.7754 0.0028 0.7948
	OS noninferiority mono/combo vs. SOC in all subjects (H9/H13)*	~352	Z statistic p-value (one-sided) Approx. observed HR	2.7754 0.0028 0.8926
	OS superiority mono/combo vs. SOC in all subjects (H10/H14)	~352	Z statistic p-value (one-sided) Approx. observed HR	2.7754 0.0028 0.7439

Timing of Analysis	Testing	Expected number of events	Value at boundary	Efficacy Boundary [†]
IA2 (interim OS analyses and final PFS analyses)				
38 mos. from study start; all 825 subjects enrolled and followed up for at least 17 months	PFS mono/combo vs. SOC in subjects with PD-L1 CPS 20 (H1/H4)	~237	Z statistic p-value (one-sided) Approx. observed HR	2.9788 0.0014 0.679
	PFS mono/combo vs. SOC in subjects with PD-L1 CPS 1 (H2/H5)	~378	Z statistic p-value (one-sided) Approx. observed HR	2.9792 0.0014 0.7358
	PFS mono vs. SOC in all subjects (H3)	~474	Z statistic p-value (one-sided) Approx. observed HR	2.9792 0.0014 0.7605
	PFS combo vs. SOC in all subjects (H6)	~474	Z statistic p-value (one-sided) Approx. observed HR	3.6331 0.0001 0.7162
	OS mono/combo vs. SOC in subjects with PD-L1 CPS 20 (H7/H11)	~205	Z statistic p-value (one-sided) Approx. observed HR	2.6398 0.0041 0.6914
	OS mono/combo vs. SOC in subjects with PD-L1 CPS 1 (H8/H12)	~332	Z statistic p-value (one-sided) Approx. observed HR	2.6425 0.0041 0.7479
	OS noninferiority mono/combo vs. SOC in all subjects (H9/H13)*	~421	Z statistic p-value (one-sided) Approx. observed HR	2.6425 0.0041 0.9272
	OS superiority mono/combo vs. SOC in all subjects (H10/H14)	~421	Z statistic p-value (one-sided) Approx. observed HR	2.6425 0.0041 0.7727

Timing of Analysis	Testing	Expected number of events	Value at boundary	Efficacy Boundary [†]
Final Analysis (Final OS Analysis)				
~ 44 mos. from study start	OS mono/combo vs. SOC in subjects with PD-L1 CPS 20 (H7/H11)	≥222	Z statistic p-value (one-sided) Approx. observed HR	2.5644 0.0052 0.7084
	OS mono/combo vs. SOC in subjects with PD-L1 CPS 1 (H8/H12)	≥359	Z statistic p-value (one-sided) Approx. observed HR	2.5641 0.0052 0.7627
	OS noninferiority mono/combo vs. SOC in all subjects (H9/H13)*	≥455	Z statistic p-value (one-sided) Approx. observed HR	2.5641 0.0052 0.9435
	OS superiority mono/combo vs. SOC in all subjects (H10/H14)	≥455	Z statistic p-value (one-sided) Approx. observed HR	2.5641 0.0052 0.7862

[†] Efficacy decision rules for OS presented in table do not account for any alpha shifting from other hypotheses as a result of a successful analysis. P-values based on spending functions determine significance of tests; hazard ratios corresponding to significance are approximate.

*NI bounds are calculated with HR=0.85 under the alternative to establish noninferiority (NI margin=1.2).

For the PFS analysis, in the scenario that events have accumulated faster than expected, event-based analysis will not allow for observing tail behavior that has been important in other trials to fully describe the treatment effect over time. For PFS hypotheses, the Lan and DeMets (1989) [62] calendar time method will be used for alpha spending to generate the group-sequential design. The timing and alpha level of the original plan will be maintained for PFS hypotheses, regardless of the number of events observed. The sample space ordering required for group sequential trials as justified by Maurer and Bretz (2013) [57] will be maintained. This ensures strong control of Type I error. The updated bounds for the PFS hypotheses are given in [Table 24](#). The bounds are based on initial alpha allocation. A Hwang-Shih-DeCani [63] (-1.073) spending function has been used to implement alpha spending for PFS hypotheses for monotherapy versus SOC in all populations (H1, H2, and H3) and combination therapy versus control with PD-L1 CPS1 and CPS20 (H4 and H5). A Hwang-Shih-DeCani (-3.079) spending function has been used for the PFS hypothesis for combination therapy versus control in all subjects (H6). The actual boundaries and the alpha level will be determined from the overall alpha level after any alpha shifting as a result of a successful analysis. The alpha level at the final analysis for the PFS hypotheses (IA2) will be calculated based on alpha reallocation, the alpha used at the interim analysis, and the actual number of events at IA1 and the final PFS analysis (IA2). The bounds given in [Table 24](#) will be adjusted accordingly.

Table 24 Decision Guidance for PFS hypotheses at Each Analysis

Timing of Analysis	Testing	Expected number of events	Value at boundary	Efficacy Boundary [†]
IA1 (interim PFS analyses)				
30 mos. from study start; all 825 subjects enrolled and followed up for at least 9 months	PFS mono/combo vs. SOC in subjects with PD-L1 CPS 20 (H1/H4)	~211	Z statistic p-value (one-sided) Approx. observed HR	3.0357 0.0012 0.6581
	PFS mono/combo vs. SOC in subjects with PD-L1 CPS 1 (H2/H5)	~337	Z statistic p-value (one-sided) Approx. observed HR	3.0357 0.0012 0.7184
	PFS mono vs. SOC in all subjects (H3)	~423	Z statistic p-value (one-sided) Approx. observed HR	3.0357 0.0012 0.7441
	PFS combo vs. SOC in all subjects (H6)	~423	Z statistic p-value (one-sided) Approx. observed HR	3.7190 0.0001 0.6965
IA2 (final PFS analyses)				
